3.2 Specific objective

- To assess the safety of 3 doses of Multi-dose Lagricel® Ofteno in patients with mild to moderate dry eye by means of the incidence of unexpected AEs related to the investigational product.

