7.4.2 Primary outcome of safety

- Incidence of AEs (ET: days 15 and 31).

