7.4.5 Definition of variables, methods and scales to be used for measurement

Variable	Type of variable	Unit (symbol)	Method of measurement	Normal value	Evaluation time	Test statistics
Primary outcome of efficacy						
OSDI	Quantitative discrete	Score	Questionnaire	< 13	BV and FV	ANOVA Student's t test*
Secondary outcome of efficacy						
TFRT with fluorescein	Quantitative continuous	Second(s)	Direct observation with slit lamp and cobalt blue filter	> 10s	BV, V1 and FV	ANOVA Student's t test*
Corneal and conjunctival staining with lissamine green	Categorical ordinal	Degrees	Direct observation with slit lamp, evaluated with Oxford's scale	0	BV, V1 and FV	Pearson's χ^2 or Fisher's exact test. McNemar's test*
Corneal and conjunctival staining with fluorescein	Categorical ordinal	Degrees	Direct observation with slit lamp, evaluated with Oxford's scale	0	BV, V1 and FV	Pearson's χ^2 or Fisher's exact test. McNemar's test*
Conjunctival hyperemia	Categorical ordinal	Grades (Efron)	Direct observation with slit lamp, evaluated with Efron's scale	0	BV, V1 and FV	Pearson's χ^2 or Fisher's exact test. McNemar's test*
Chemosis	Categorical nominal	Present/absent	Observation	Absent	BV, V1 and FV	Pearson's χ^2 or Fisher's exact test. McNemar's test*
Primary outcome of safety						
AE	Quantitative discrete	Number of Cases (N)	Count	0	BV, V1 and FV	ANOVA
AE(bis)	Categorical nominal	Present/absent (-)	Observation	Absent	BV, V1 and FV	Pearson's χ^2 or Fisher's exact test.
BCVA	Quantitative discrete	Fraction (-)	Snellen chart	1	BV, V1 and FV	ANOVA Student's t test*
IOP	Quantitative discrete	Number	Tonometry	≥ 10 and ≤ 21	V1 and FV	ANOVA Student's t test*

OSDI, ocular surface disease index; TFRT, tear film rupture time; AEs, adverse events; BCVA, better corrected visual acuity; IOP, intraocular pressure; ANOVA, Analysis of Variance; χ^2, Chi-square. *When applicable.
						

Table 3. Operational definition of variables

The variables, method, and scales for their measurement are described in detail below. They are in order according to Table 3.

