10.1.2 Data interpretation

The Kolmogorov-Smirnov and Shapiro Wilk tests will be performed, as appropriate, to determine if the distribution is normal in the results obtained in each study group [59].

The results of the continuous quantitative variables will be presented in measures of central tendency: mean, standard deviation and/or range.

- Intragroup analysis: Differences within groups will be analyzed using the one-way ANOVA or the Student's t-test when applicable.
- Inter-group analysis: For equal variances, Tukey's post-hoc test will be used, otherwise Dunnett's statistic will be used. Student's t-test will be used when applicable.

The level of difference to consider significance will be an alpha (α) of 0.05 or less. A 95% confidence interval (95% CI) will be considered for non-inferiority criteria [60].

The result of the nominal and ordinal qualitative variables will be presented in frequencies, proportions and percentages.

The statistical analysis to identify significant differences in the qualitative variables will be carried out by creating 2x2 contingency tables and will be carried out as follows:

- Intra-group difference: McNemar test. This is applied to 2x2 contingency tables with a dichotomous feature, with pairs of paired subjects, to determine if the marginal frequencies of row and column are equal (marginal homogeneity).
- Difference between groups: Pearson's Chi-square test (X^2) or Fisher's exact test at expected values less than 5.

The level of difference to consider significance will be an alpha (α) of 0.05 or less.

For the reporting of AEs, all eyes of those participants who were randomly assigned to an intervention group after the baseline visit will be considered. The results will be expressed in number of subjects.

The final report of the results will be shown in tables or graphs, as appropriate.

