10.1.3 Procedure for handling missing data

Safety: The safety assessment will include in the analysis all those subjects (both eyes) who have been exposed at least once to the intervention, regardless of the visit in which they were eliminated from the study (ITT; *Intention To Treat* population).

Efficacy: Those subjects who meet a minimum adherence of 70% will be included in the statistical analysis to meet the objective of the study, taken from the weight of the IP. In cases where the container is not returned, or it has not preserved its physical integrity, adherence will be measured by means of the subject's diary.

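### The single primary safety outcome has two operational definitions in Table 3, each with its own 0.05 test, and nothing says which one is the main analysis

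*Combined protocol and SAP*

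**What the plan says.** Section 7.4.2 states the primary safety outcome as "Incidence of AEs (ET: days 15 and 31", without saying whether events, eyes or subjects are counted. Table 3 in section 7.4.5 then gives it two rows:

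- **AE:** quantitative discrete, measured by counting, with unit "Number of Cases (N", compared by ANOVA.
- **AE(bis):** categorical nominal, "Present/absent", compared by Pearson's chi-square or Fisher's exact test.

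Section 10.1.2 sets significance at 0.05 with no order between the two rows, and analyses qualitative variables in 2x2 tables although there are three arms. For AE reporting it considers "all eyes of those participants who were randomly assigned to an intervention group", and adds: "The results will be expressed in number of subjects".

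Two neighbouring statements do not line up with these. Section 10.1.3 bases safety on "all those subjects (both eyes) who have been exposed at least once to the intervention", whereas section 10.1.2 speaks of randomised participants. The specific objective in section 3.2 assesses safety "by means of the incidence of unexpected AEs related to the investigational product", which is narrower than all AEs.

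**The concern.** Reporting both events and affected subjects is ordinary practice. Here, however, both rows carry an inferential test under one primary outcome, and section 10.1.1 sends the analyst to Table 3 to classify the variables. Both tests can therefore be run as planned, and the plan has no rule for the case where they disagree.

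The rows estimate different things. Row AE compares the mean number of cases per subject, so a subject with four cases weighs four times as much as a subject with one. AE(bis) compares the proportion of subjects affected. Nor is there a counting rule for row AE. Staining, for example, is graded per eye and at more than one visit, and becomes an AE at a threshold (sections 7.4.5.3 and 7.4.5.4), but nothing says whether a bilateral or persisting finding is one case or several. What is at stake is whether the statement about AEs by dosage is fixed before the data are seen.

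**Working it through.** The plan gives no AE rate, power or sample size for safety, so there is no safety figure to reproduce. The inputs from the plan are three arms, 47 subjects per arm (section 10.2) and alpha 0.05 (section 10.1.2). All AE frequencies below are assumptions.

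**Step 1: can the two tests reverse on the same data?** Two constructed data sets, 47 subjects per arm in the order BID, QID, 6x/D.

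*Same subjects, different cases.* In each arm 8 subjects have an AE, with 1, 1 and 4 cases each, giving 8, 8 and 32 cases.
- Arm means are 8/47 = 0.170, 0.170 and 32/47 = 0.681; the overall mean is 48/141 = 0.340.
- Between-arm sum of squares: 47 × (0.170² + 0.170² + 0.340²) ≈ 8.17.
- Within-arm sum of squares: 2 × (8 − 8²/47) + (128 − 32²/47) ≈ 13.28 + 106.21 = 119.49.
- F = (8.17/2)/(119.49/138) ≈ 4.72, p = 0.010.
- Chi-square on 8/8/8 subjects: p = 1.00.

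*Same cases, different subjects.* Each arm has 16 cases, coming from 4, 8 and 16 subjects.
- ANOVA: equal means, p = 1.00.
- Chi-square: 28 of 141 subjects are affected, so 28/3 = 9.33 affected and 37.67 unaffected are expected per arm. The squared deviations sum to 28.44 + 1.78 + 44.44 = 74.67. X² = 74.67/9.33 + 74.67/37.67 = 8.00 + 1.98 = 9.98 on 2 df, p = 0.007.

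The verdict can therefore reverse in either direction.

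**Step 2: how often would they differ?** Simulation with AE status per subject ~ Bernoulli(p) and cases given an AE = 1 + Poisson(λ). Pearson chi-square (3x2) is applied to status and one-way ANOVA to cases, each at 0.05.

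| Assumption | Chi-square rejects | ANOVA rejects | Either rejects | Verdicts differ |
|---|---|---|---|---|
| No difference, p = 20-50% | about 5% | about 5% | about 7-8% | about 4-6% |
| Incidence 20/30/45%, λ = 1 in all arms | about 65% | about 51% | – | about 20% |
| Incidence 30% in all arms; mean cases per affected subject 1.5/1.5/3 | about 5% | about 45% | – | – |
| Incidence 30% in all arms; mean cases 1.5/1.5/2 | about 5% | about 11% | – | – |
| Incidence 10% in all arms; mean cases 1.5/1.5/3 | about 5% | about 11% | – | – |

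In the last three rows the share of affected subjects is equal, but the case burden truly differs. ANOVA is detecting that difference.

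**Step 3: which row matches the named outcome?** Section 7.4.2 says incidence and section 10.1.2 reports in subjects. AE(bis) satisfies both. A mean number of cases satisfies neither.

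**The case against.** The best defence is that the plan already leans towards the subject level: the outcome is called an incidence and results are given in subjects. In addition, no safety hypothesis, margin or sample size depends on either test. Sections 3.4 and 10.2 concern OSDI only, and the one numerical safety threshold, serious AEs in more than 10% of participants in a group (section 11.3), is already a proportion of participants. This stands, and it limits the consequence. It does not remove the ANOVA row, which still tests the same primary outcome with equal standing.

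Three stronger readings are tempting and are not supported.

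- A reader might take the eyes/subjects statement in section 10.1.2 as a third definition, with eyes tested as if independent. No test is attached to it. Its natural sense is that both eyes are examined and the subject is counted, which is AE(bis), and section 10.1.3 uses the same convention. The plan does not say so outright, so a clarification is still useful.
- A reader might infer that instillation symptoms will push up the case count at six applications a day. Section 7.4.5.7 lists such symptoms as expected, while the objective in section 3.2 concerns unexpected related AEs. No text makes each recurrence a separate case, and section 8.1.4 records an AE with onset and outcome dates and, if applicable, the eye.
- A reader might quote the 45% as a false-positive rate. It comes from an assumed true difference in case burden and falls to about 11% under milder assumptions.

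**Conclusion.** The concern holds as a two-way conflict: one primary safety outcome, two definitions, two tests at 0.05 and no hierarchy. Only AE(bis) is an incidence. Under no difference the cost is modest: about 7-8% for at least one rejection instead of 5%. The larger issue is that the two rows answer different questions. Their verdicts differ in about 20% of trials at an assumed 20/30/45% incidence, and they can reverse completely in constructed data. All of these figures rest on assumed AE rates, a Poisson model for repeat cases and 47 analysed subjects per arm. The simulation models neither eyes nor visits, so it does not quantify bilateral or repeat-visit counting. The efficacy conclusion is unaffected. The point deserves correction because the safety statement should not depend on a choice left open until after the data are seen, and the correction costs very little.

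**What to change.** In sections 7.4.2, 7.4.5 (Table 3) and 10.1.2:

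1. Make AE(bis) at subject level the primary safety outcome: subjects with at least one AE in either eye, each counted once, divided by subjects exposed at least once, as in section 10.1.3.
2. Compare the three dosages in one 3x2 table by chi-square, or by Fisher's exact test where expected counts are small, in place of 2x2 tables.
3. Report the number of cases per subject and per arm descriptively, and remove ANOVA on cases as a test of the primary safety outcome.
4. Reword section 10.1.2 to say that both eyes are examined and the subject is the unit, and align its randomised set with the exposed set of section 10.1.3.
5. Reconcile all AEs (section 7.4.2) with unexpected, product-related AEs (section 3.2), stating which is primary.

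The cost is wording only, with no new data. The formal test on case counts is lost; the counts themselves remain reported.

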10.1.3 Procedure for handling missing data

Safety: The safety assessment will include in the analysis all those subjects (both eyes) who have been exposed at least once to the intervention, regardless of the visit in which they were eliminated from the study (ITT; *Intention To Treat* population).

Efficacy: Those subjects who meet a minimum adherence of 70% will be included in the statistical analysis to meet the objective of the study, taken from the weight of the IP. In cases where the container is not returned, or it has not preserved its physical integrity, adherence will be measured by means of the subject's diary.

10.1.4 Deviations from the statistical plan

According to the calculation of the sample size to meet the primary objective of the study, 141 evaluable subjects (47 subjects per dosage) are required. If this number is not met due to a loss of subjects greater than 20% contemplated in this protocol (loss of follow-up or withdrawal of ICF), in order to balance the treatment groups, the sponsor may replace these subjects.

The results obtained from the substituted subjects will continue to be used for safety analysis and will be part of the *Intention To Treat* population (ITT).

10.1.5 Subjects included in the analysis

Those subjects who meet a minimum adherence of 70% by weight and 70% per diary will be included in the statistical analysis to meet the primary endpoint of the study (*Per protocol* population, PP).

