6.4 Procedure for monitoring and measuring adherence

For more than four decades, research has been conducted on the appropriate way to measure and quantify medication adherence, but none is considered the gold standard in both cross-sectional and longitudinal studies. [40, 41, 42, 43, 44, 45, 46, 47] There are different procedures to measure adherence to pharmacological interventions. The most common procedure is self-reporting, which includes: patient interviews, questionnaires and self-monitoring diaries. Its strengths are speed, flexibility, low cost and ease of implementation; They have a high degree of specificity for non-adherence, but the sensitivity and reliability for adherence is low. [47, 48] The biochemical measurement of the drug, or its metabolite, are methods that better confirm the use of the drug; but it raises costs, is impractical and of little use in ophthalmic applications, since concentrations at the peripheral level could be undetectable; samples of other tissues involve more invasive methods that would not be advisable. [47]

Medication counting is another way to measure adherence. Classically referred to as "pill counting," in ophthalmology it translates to the weight of the bottle. This is a simple, inexpensive, and non-invasive method.

The main disadvantages of this method are:

1. The application of the medication cannot be confirmed (it may have been intentionally pulled or instilled outside the eye)
2. It depends on the subject bringing back the medication. [47, 48]

However, in this study, the initial and final weight of the bottle will also be taken into account to measure adherence, at the same time adherence will be measured through the subject's diary.

A multi-procedure approach to measuring adherence is recommended. Because there is no measurement of ideal adherence, it is appropriate to use more than one method when trying to achieve results that resemble reality. Selecting two or more methods allows their strengths and weaknesses to be compensated, to capture adherence levels more accurately. [46]

The evaluation of adherence will be favored by means of the weight of the bottle and will be carried out in the following way, taking into account the following information: the weight of the drop, the initial weight of the container, the final weight of the container and the calculation of the total applications. The following simplified formula shall be used:

$$Ad = \frac{(P_i - P_f)100}{PT}$$

Where:

Ad = adherence

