P_i = weight of the container delivered to the subject at the beginning

P_f = weight of the container returned by the subject

PT = weight of the dosage indicated for the intervention

$$PT = (P_g)G$$

Where:

P_g = weight of one drop of the intervention, determined by the research and development department

G = number of applications indicated for the intervention

Packaging that does not retain its physical integrity will not be considered for the calculation of adherence. In cases where the container is not returned, or it has not preserved its physical integrity, adherence will be measured only through the subject's diary

Adherence through the subject's diary will be measured as follows:

$$Ad = (Ar)100/Ai$$

Ad = Adhesion

Ar = Registered Applications

Ai = Applications indicated for the products under investigation

There is no standardized parameter to define adequate adherence, it must be defined and delineated by the objectives of the particular research. [47]

For this study, a minimum adherence of 70% will be considered to be what is necessary to meet the objectives of the research both by subject diary and by bottle weight. Therefore, subjects who have an adherence of less than 70% will not be considered for the efficacy analysis, they will only enter the safety analysis.

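### Every efficacy result, including the primary OSDI endpoint, is limited to subjects with at least 70% adherence; none keeps the groups as randomised, and the adherence rule is defined in conflicting ways

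*Combined protocol and SAP*

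**What the plan says.** - **Section 10.1.5** gives the per-protocol population for the primary endpoint: "Those subjects who meet a minimum adherence of 70% by weight and 70% per diary will be included in the statistical analysis". Both measures are required.
- **Section 10.1.3** gives the efficacy population with one criterion: "Those subjects who meet a minimum adherence of 70% will be included in the statistical analysis to meet the objective of the study". The figure comes from the weight of the product. If the bottle is not returned or is damaged, "adherence will be measured by means of the subject's diary".
- **Section 6.4** contains both ideas. It prefers weight ("The evaluation of adherence will be favored by means of the weight of the bottle"), then describes 70% as "what is necessary to meet the objectives of the research both by subject diary and by bottle weight". It applies the exclusion to all efficacy: "subjects who have an adherence of less than 70% will not be considered for the efficacy analysis, they will only enter the safety analysis".
- **The set called ITT** appears under safety in 10.1.3: "The safety assessment will include in the analysis all those subjects (both eyes) who have been exposed at least once to the intervention". Section 10.1.4 adds that the results of substituted subjects "will continue to be used for safety analysis and will be part of the" ITT population.
- **Section 10.1.2** refers to all randomised participants, but only for adverse event reporting.

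No section plans an OSDI or secondary efficacy result in all randomised subjects, even as a sensitivity analysis.

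**The concern.** The trial is meant to find the ideal dosage (2.4.2, 2.5.1, 4.2), and the randomised factor is how often the drops are used. Adherence is observed after randomisation and, under 7.4.6.3, is calculated against each arm's own daily number of applications. If failure of the 70% rule differs between arms and is related to symptoms, the remaining subjects are no longer comparable groups. Their comparison then does not estimate the effect of assigning a dosage, and the plan offers no other efficacy result to set beside it.

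The selection also reaches the hypothesis in 3.4, a 20% OSDI decrease in at least one dosage, because each arm's decrease is computed without its non-adherers.

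Separately, two membership rules for the same set mean that the primary population could be chosen after the data are seen.

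**Working it through.** **1. The two rules side by side**

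| Subject | 10.1.3 | 10.1.5 |
|---|---|---|
| Intact bottle, weight and diary both at least 70% | in | in |
| Intact bottle, weight at least 70%, diary below 70% | in | out |
| Intact bottle, weight below 70% | out | out |
| Bottle missing or damaged, diary at least 70% | in | out if read literally; in if the fallback in 6.4 is carried over |

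**2. What 70% means in each arm**

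Over 30 days the arms are assigned 2 × 30 = 60, 4 × 30 = 120 and 6 × 30 = 180 applications, so the cut-offs are 42, 84 and 126. A subject making four applications a day (120 in total) scores 120/180 = 67% in 6x/D and is excluded, but 120/120 = 100% in QID and is kept. The formula has no upper limit: the same use in BID scores 120/60 = 200% and is kept.

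**3. Group size**

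Section 10.2.2 reproduces: 39 × 1.20 = 46.8, rounded to 47; 47 × 3 = 141. I take 47 per arm as randomised, although 10.1.4 and 10.2.1 call these subjects evaluable.

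**4. Illustration of the between-arm effect**

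All inputs other than 47 are assumed: failure f of 5%, 12% and 25% in BID, QID and 6x/D; those failing end g = 3 or 8 OSDI points worse; SD 6, 8, 10 or 12; one-way ANOVA at 0.05; 20,000 simulated trials per setting (simulation error about 0.15 percentage points).

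- Model A: arms equal in all randomised subjects. The adherent mean is lower by f × g, so 6x/D minus BID is −(0.25 − 0.05) × g = −0.6 or −1.6.
- Model B: arms equal in adherers. The all-randomised mean is higher by f × g, so 6x/D minus BID is +0.6 or +1.6.

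Where four rejection rates are listed, they are for SD 6, 8, 10 and 12.

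| Model, gap | Difference, adherent set | Difference, all randomised | Rejection, adherent set | Rejection, all randomised |
|---|---|---|---|---|
| A, 3 | −0.6 | 0 | 6.5, 5.8, 5.5, 5.2% | 4.8–5.2% |
| A, 8 | −1.6 | 0 | 19.2, 11.8, 8.8, 7.8% | 4.8–5.2% |
| B, 3 | about 0 | +0.6 | 4.5–5.2% | 6.9, 5.8, 5.6, 5.5% |
| B, 8 | about 0 | +1.6 | 4.5–5.2% | 19.4, 12.9, 10.1, 8.2% |

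Under Model A with SD 8, equal 15% failure (gap 8) rejects in 5.1%, and no gap rejects in 5.0%.

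A second form gives the same pattern. Here a normal outcome is correlated with adherence, the arms are equal when all are analysed, and 5%, 15% and 30% are excluded. Rejection is 5.6%, 7.0% and 11.1% at correlations 0.2, 0.3 and 0.5, with 6x/D and BID separated by 0.08, 0.12 and 0.19 SD. With 10% excluded in every arm it stays near 5%.

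**5. Illustration of the 20% criterion**

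The midpoint of the entry range in 5.1.1 is (13 + 32)/2 = 22.5, and 20% of that is 4.5 points. If adherers average exactly 20%, the all-randomised decrease is (4.5 − f × g)/22.5:

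| f | g = 3 | g = 8 |
|---|---|---|
| 5% | 4.35/22.5 = 19.3% | 4.10/22.5 = 18.2% |
| 12% | 4.14/22.5 = 18.4% | 3.54/22.5 = 15.7% |
| 25% | 3.75/22.5 = 16.7% | 2.50/22.5 = 11.1% |

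If those failing do better instead, the range runs from (4.5 + 0.15)/22.5 = 20.7% to (4.5 + 2.0)/22.5 = 28.9%.

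**The case against.** **The 8-point gap is probably too wide.** The study cited in 10.2.2 reports −19.66% on hyaluronic acid and +12.47% on saline, a contrast of 32.13%, or about 7.2 points at a baseline of 22.5. An 8-point gap makes partial users differ from adherers by more than active differed from saline. That study used another product in mild disease, so it does not set a limit, but the objection stands: the gap-8 figures are an outer case. At 3 points the rejection rate stays between 5.2% and 6.9% and the shift is 0.6 points.

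**The adherent set answers a legitimate question.** How a dosage works when it is taken is a fair phase II question, and under Model B that set keeps its nominal error rate. Non-inferiority wording (10.1.2, 10.2.2) strengthens the case, because including non-adherers can pull arms together. This justifies keeping the adherent analysis. It does not justify having no other.

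**The 20% hypothesis is a within-arm change**, which randomisation does not make causal. That is correct; the concern there is selection of who is counted.

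**The rule conflict is narrow, and 10.1.1 masks the statistical staff to group.** Both are true. Masking limits choices that favour a known arm, but it does not decide who belongs in the primary set or restore the randomised groups.

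**Keeping substituted subjects in the ITT set is proper.** Agreed. The fault is that this set is not used for efficacy.

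**Conclusion.** The concern holds and should be fixed before analysis. Followed as written, the plan yields no efficacy comparison of the randomised groups and no unique primary population. Both conclusions rest on the text alone.

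The size of any distortion cannot be derived from the documents. It requires failure rates that differ by arm and a link between failing and OSDI; without either, the between-arm comparison is not distorted. Under the assumed failure rates, the two sets differ by 0.6 points at a 3-point gap and 1.6 points at an 8-point gap. The first is small, and the second rests on an input that is probably too large. Neither model shows that the adherent set is always the wrong one. They show that the two sets answer different questions and that only one is planned.

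**What to change.** 1. Add an efficacy analysis of all randomised subjects in their assigned dosage, whatever their adherence, using the day-31 OSDI already scheduled. Make it the main analysis for between-dosage differences and report each arm's percent OSDI decrease in it. Define the set explicitly, since the ITT set in 10.1.3 is defined by exposure, and state in advance how a missing day-31 OSDI is handled.
2. Keep the 70% adherence set as a supporting analysis, reported alongside for any non-inferiority statement.
3. Reconcile 6.4, 10.1.3 and 10.1.5 to one adherence rule, fixed before data are seen, and report the number excluded in each arm.

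The cost is a protocol amendment with committee review and regulator authorisation (11.2), plus one extra analysis with a chosen missing-data method. No visits or measurements are added. The estimate in all randomised subjects may be diluted relative to adherers.

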6.3 Concomitant treatments and medications not authorized during the study

Unauthorized medicines will not be allowed during the intervention period, including the period between the end of BV and D1, from D1 the IP application scheme will begin. The objective of this restriction is to avoid drug interactions that could alter the results of the variables evaluated.

Medications allowed: Ophthalmic: Tetracaine 0.5%, Tropicamide 0.8% / Phenylephrine 5% (for study procedures) and IP. Non-ophthalmic: Hormonal contraceptives. At the discretion of the investigator, systemic medicines whose effects do not modify the efficacy or safety parameters of this protocol may be used, but must be reported to the sponsor's scientific committee to determine the participant's status as appropriate.

Prohibited Drugs: Any ophthalmic drugs that are not on the list of allowed drugs. Systemic medications: steroids, immunomodulators, and tetracyclines.

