7.4.6.3 Follow-up visit

- Concomitant Drug Evaluation: See 7.4.6.2
- Vital Signs: See 7.4.6.2
- BCVA: See 7.4.5.8
- Tear Film Rupture Time: See 7.4.5.2
- Ocular Surface Staining: See 7.4.5.3 and 7.4.5.4
- Comprehensive ophthalmologic evaluation: See 7.4.6.2
- IOP: 7.4.5.9
- AE Evaluation: Ver 7.4.5.7
- Adherence assessment: Adherence will be assessed in two ways, one through the initial vs. final weight of the medication bottle and the other through the record of applications in the subject's diary, adherence will be calculated. Adherence will be calculated based on the dosage of 2, 4 and 6 applications per day.

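### The per-protocol set for the primary endpoint has a 70% adherence floor but no upper limit and no exclusion for prohibited eye drops, so subjects who departed from their assigned treatment are analysed as per protocol

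*Combined protocol and SAP*

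**What the plan says.** The rule for the efficacy set appears three times, each time as a minimum only.

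- Section 10.1.5, which names the per-protocol population and ties it to the primary endpoint: "Those subjects who meet a minimum adherence of 70% by weight and 70% per diary will be included in the statistical analysis".
- Section 10.1.3, which relies on bottle weight and uses the diary only when the bottle is missing or damaged: "Those subjects who meet a minimum adherence of 70% will be included in the statistical analysis to meet the objective of the study".
- Section 6.4, which gives the only stated reason for leaving the efficacy analysis: "subjects who have an adherence of less than 70% will not be considered for the efficacy analysis".

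Section 6.4 defines adherence as a percentage of what was assigned, by bottle weight and by diary. The weight denominator is the weight of one drop times G, where "G = number of applications indicated for the intervention". Section 7.4.6.3 adds: "Adherence will be calculated based on the dosage of 2, 4 and 6 applications per day". Neither ratio is capped at 100%.

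Section 6.3 lists what is not permitted: "Prohibited Drugs: Any ophthalmic drugs that are not on the list of allowed drugs". The allowed ophthalmic list contains only the agents used for study procedures and the investigational product, so any other lubricant is prohibited. The stated purpose is to keep other drugs from altering the measured variables. No analysis consequence is attached.

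**The concern.** A set labelled per protocol should contain subjects who took what they were assigned and nothing that the protocol forbids. Here the three arms use one product at 2, 4 and 6 applications a day, and the study aims to establish the ideal dosage (2.4.2, 4.2). Frequency is the whole contrast, so actual frequency and other lubricants are the departures that matter most. The trial is open-label, and 6.1.2.1 notes that lubricants are generally prescribed as needed, so extra drops are foreseeable.

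Two things are at stake. In comparisons between dosages, subjects whose real use resembles another arm's pull the arms together. That pull is in the favourable direction if a non-inferiority reading (10.1.2, 10.2.2) is made. For the hypothesis in 3.4, a 20% fall in OSDI in at least one dosage, extra drops or a second product could credit a dosage with a fall it did not produce. Efficacy is analysed in no other set: the ITT population is tied to safety (10.1.3, 10.1.4).

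**Working it through.** **Plan figures.** The plan states no rate of overuse or of prohibited-drop use, so there is none to reproduce. The one plan figure that a narrower set touches is the loss allowance in 10.2.2: 39 x 1.20 = 46.8, rounded to 47 per arm (8 extra), and 47 x 3 = 141.

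**Inputs.** 2, 4 and 6 applications a day (7.4.6.3); 30 days of treatment (6.1); floor 70% (6.4, 10.1.5); diary adherence = 100 x recorded / indicated applications (6.4).

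**1. Does overuse pass the rule?** By diary, if every application is recorded:

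| Arm | Indicated in 30 days | Floor per day | Score at 4/day | Score at 6/day |
|---|---|---|---|---|
| BID | 60 | 0.7 x 2 = 1.4 | 120/60 = 200% | 180/60 = 300% |
| QID | 120 | 0.7 x 4 = 2.8 | 100% | 180/120 = 150% |
| 6x/D | 180 | 0.7 x 6 = 4.2 | 120/180 = 66.7% | 100% |

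Every score above 70% is admitted to the assigned arm. A BID subject reaches the accepted QID range at 2.8/2 = 140%, and a QID subject reaches the accepted 6x/D range at 4.2/4 = 105%.

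**2. By weight.** Dosing is in both eyes, but 6.4 multiplies the weight of one drop by the number of applications. If G counts drops to both eyes, the diary figures above carry over. If it does not, full use scores 200%, a BID subject instilling four times a day scores 400%, and the 70% floor is met at 35% of the indicated drops. The weight figure cannot be read until G is defined.

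**3. Does anything remove users of prohibited eye drops?** Read together:
- 6.3 forbids the drugs but states no consequence for analysis. Its referral to the sponsor's scientific committee concerns systemic medicines used at the investigator's discretion.
- 10.1.3 mentions subjects eliminated from the study, but no elimination criteria are given.
- 10.1.5 is a complete inclusion rule with adherence as its only condition.

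As written, such a subject stays in.

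**4. What dilution would do, for illustration only.** Assume that a share f of one arm responds exactly like the comparator arm, and that the undiluted contrast has 80% power (two-sided 5%) at 39 per arm. The contrast shrinks to (1 - f), power is approximately Phi((1 - f) x 2.80 - 1.96), and the required n grows by 1/(1 - f)^2.

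| f | Power at 39 per arm | Factor on n |
|---|---|---|
| 5% | 75.9% | 1.11 |
| 10% | 71.3% | 1.23 |
| 20% | 61.1% | 1.56 |

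These values of f are assumptions. The plan's own sample size rests on two proportions, so these are not the trial's power figures.

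**The case against.** The strongest objection is to the obvious remedy. A reader might infer that the per-protocol set needs a fixed two-sided window such as 70-130%. The documents do not support that, for four reasons:

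- The ceiling is arbitrary. It would separate BID (at most 2.6 a day) from QID (at least 2.8), but QID and 6x/D would still overlap from 4.2 to 5.2 a day. Most of that overlap comes from the 70% floor: 6x/D at its floor is 4.2 a day, against 4.0 for full QID use.
- It would lean on bottle weight, which 6.4 itself says cannot confirm that drops reached the eye, and on a G that is not defined for both eyes.
- BID subjects who top up may be those for whom BID was not enough. Dropping them could flatter BID, which is selection on outcome after randomisation.
- Efficacy is already confined to adherent subjects, so narrowing the only efficacy set without an all-randomised analysis increases the dependence on selection.

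All four stand, and they shape the fix below.

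A second objection is that the prohibited-drop point argues from silence, since 6.3 forbids these drugs and 10.1.3 contemplates elimination. This does not hold: with no elimination criteria and a complete inclusion rule, the silence leaves these subjects in. It is fair that a topical steroid is an unlikely case, because patients needing stage 2 treatment are excluded at entry (5.2.1). Another lubricant is the realistic example.

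Third, direct questioning (6.5) and the adherence check at the follow-up visit (7.4.6.3) may reduce overuse. They do not change who is analysed.

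**Conclusion.** The gap is real. The only set used for efficacy has no upper adherence limit, no exclusion for prohibited ophthalmic drugs and no requirement that eligibility was met. It therefore admits subjects whom the trial's own records would show to have departed from the assigned treatment. The effect can be to blur the dosage comparison or to credit a dosage with benefit it did not produce.

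Two stronger readings are tempting but unsupported. One is that the dosage comparison is biased toward no difference by a calculable amount. That needs a rate of overuse, full crossover to the other dosage's response and a real frequency-response difference, and the documents give none of these. The other is that topping up concentrates in the BID arm. That is a reasonable inference in an open-label trial, but nothing in the documents establishes it. The size is therefore unknown. The conclusion rests on the wording of the inclusion rule and, for the percentages, on extra applications being recorded in the diary.

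**What to change.** 1. In 10.1.5, exclude from the per-protocol set subjects who used prohibited ophthalmic medication between BV and FV, and subjects who did not meet the eligibility criteria. Decide these exclusions before group codes are revealed; 10.1.1 already keeps the analysts blinded to group.
2. Report actual applications per day by arm, from the diary and from bottle weight, with G defined for both eyes. At the same time reconcile 10.1.5 (weight and diary) with 10.1.3 (weight, diary as fallback).
3. Handle overuse in a pre-specified sensitivity analysis that excludes subjects whose recorded use falls in another dosage's range, not by a fixed ceiling in the main set. State the boundary for each arm: the next arm's floor is 140% for BID but only 105% for QID, which would catch trivial excess; the next arm's full frequency is 200% and 150%.
4. Show an efficacy analysis of all randomised subjects alongside, so that the exclusions do not carry the conclusion alone.

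**Cost.** Analysis wording and a few extra tables. Diary, bottle weight and concomitant medication are already collected (1.3, 6.4). The per-protocol set becomes somewhat smaller. The 20% allowance and the replacement rule name only loss to follow-up and consent withdrawal (5.2.2, 10.1.4), so they do not cover these exclusions. There is no slack either: a full 20% loss from 47 leaves 47 x 0.8 = 37.6, already below 39.
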